7.4 Study size

This study is intended to collect long-term safety follow-up information and the sample size estimate is not based on statistical measures. Every effort will be made to enroll all patients treated with voretigene neparovec, and it is expected that a minimum of 40 adult or pediatric patients can be enrolled over a five-year enrollment period.

7.5 Data management

7.5.1 Data Collection

Data will be entered from patient source documents to case report forms (CRF) that are specifically designed for this study. Data will be retained based on local regulatory requirements or the terms in the clinical trial agreements, whichever is longer.

7.5.2 Data management

Novartis Data Management or a designated CRO will assure database quality processes are followed including review of the data entered into the CRFs by investigational staff for completeness and accuracy, and in accordance with the data validation plan.

7.6 Data analysis

This study is intended to descriptively document the frequency and severity of events of interest related to voretigene neparovec (vector and/or transgene), the subretinal injection procedure, the concomitant use of corticosteroids, or a combination of these procedures and products. The Full Analysis Set (FAS), defined as all individuals for whom an informed consent/assent was signed and who are enrolled in the study and received at least one injection of voretigene neparovec, will be used to summarize all data.

Continuous variables will be summarized in terms of mean, standard deviation, median, minimum and maximum. Other descriptive statistics (e.g., quartiles, coefficient of variation) may be reported when appropriate. Categorical variables will be summarized using frequency

counts and percentages. Unless otherwise noted, the denominator for the percentages will include all patients in the FAS population.

The unit of analysis for disposition, demographics and baseline diagnoses will be patient; the unit of analysis for ophthalmic examination findings will be right eye and/or left eye. The unit for non-ocular AEs will be patient; the unit for ocular AEs will be eye(s). The unit for other variables will be patient or eye(s) as appropriate.

Analyses to assess the impact of subgrouping based on selected variables which become of interest during the study will be performed as defined in the Statistical Analysis Plan (SAP).

Interim data assessments will occur at a minimum, on an annual basis and will be included in annual progress reports. A complete description of the statistical analyses and methods will be available in the SAP.

7.6.1 Demographics, baseline disease characteristics, disposition, ophthalmic examination findings, and other variables

Descriptive summary statistics will be provided for demographics and pre-treatment/baseline disease characteristics. Descriptive summary statistics will also be provided for ophthalmic examination results (e.g., VA, VF, FST, and OCT) at pre-treatment/baseline and post-administration. Ophthalmic examination results will be presented by age categories. Patient- and caregiver-reported outcomes will be summarized at pre-treatment/baseline and annually for questionnaire overall and subscale scores presented as percentages. Disposition, including number of patients enrolled in the study at the time of each analysis, will be tabulated; demographic characteristics will also be re-summarized at each analysis point.

The unit of analysis for disposition, demographics and pre-treatment/baseline diagnoses will be patient; the unit of analysis for ophthalmic examination findings will be right eye and/or left eye. The unit for non-ocular AEs will be patient; the unit for ocular AEs will be eye(s). The unit for other variables will be patient or eye(s) as appropriate.

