7.2 Setting

This is a non-interventional study and does not impose a therapy protocol, diagnostic/therapeutic procedure, or a visit schedule. Patients will be treated according to the local prescribing information and routine medical practice in terms of visit frequency and types of assessments performed and only these data will be collected as part of the study.

Every effort will be made to enroll all patients treated with voretigene neparovec, and it is expected that a minimum of 40 adult or pediatric, male or female patients can be enrolled over a five year enrollment period. Patients will be followed for five years following administration of voretigene neparovec.

Patients will be enrolled based on the selection criteria described below. Participation in the study is voluntary but strongly encouraged to enroll all patients treated with voretigene neparovec.

Selection criteria:

1. Is planning to receive or has received voretigene neparovec in at least one eye.
2. Provided informed consent/assent to participate in this study.
3. Has not previously participated and is not currently participating in an interventional clinical trial with voretigene neparovec.

Patients who planned to be treated or have been treated with voretigene neparovec will be informed of this study by qualified study sites. After informed consent/assent is provided, data (including any relevant pre-existing data collected prior to informed consent) will be collected in this registry-based study.

Qualified study sites will be primarily Luxturna[®] treatment centers where qualified staff (i.e., vitreoretinal surgeons and pharmacists) have participated in the mandatory educational program about use of the product, and inherited retinal dystrophy (IRD) referral centers. Preferably, patients are followed up at the same Luxturna[®] treatment center or IRD referral center where they were enrolled, for consistency of data collection. If more than one center is involved in the

treatment and follow-up of a patient (e.g. a treatment center and a referral center), then enrollment into the study should take place at the site where the patient will be seen most frequently and data from all other centers will be collected at this study site.

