A patient will be considered potentially lost to follow-up if they do not return to the study site for the annual follow-up visits and no information can be obtained via telephone contact or other sources. The site is encouraged to make every effort (phone, email, certified mail) and document those efforts to regain contact to resume data collection. A patient cannot be considered as lost to follow-up until the time point of their scheduled End of Study visit has passed.

Variables

The safety profile of voretigene neparvovec, administered to patients who enroll in this study, should be evaluated based on the examination of general demographic and safety variables, including specific clinical measures.

Pre-treatment and Baseline characteristics

- Demographics (e.g. age, gender, race, ethnicity, and country of residence)
- Medical and surgical history (including prior gene and cell therapy)
- Ocular characteristics (including information on viable cells and ophthalmic exam results)
- Genetic diagnosis related to the inherited retinal dystrophy
- Clinical diagnoses related to the inherited retinal dystrophy
- Concomitant medications and procedures
- PRO and caregiver questionnaires

Voretigene neparvovec administration information

- Surgical center location
- Date of injection(s) (right eye, left eye)
- Lot number and volume administered (right eye, left eye)
- Details of perioperative corticosteroids use
- Surgical details including number and location of retinotomies (right eye, left eye)

Safety Variables

- The following events are designated as AESIs and will be queried through the standardized safety questionnaire ([Section 12.1](#)) and entered into the AE CRF:
 - Ocular AEs
 - Lack of efficacy and/or decline in efficacy over time*
 - Third-party transmission
 - Host immune response
 - Development or exacerbation of oncologic, hematologic, neurologic, or auto-immune diseases
- ***Note:** Signs and symptoms resulting from “lack of efficacy” or “decline of efficacy over time” or “failure of expected pharmacological action” should be provided in the AE or SAE description.
- Follow-up information on reported chorioretinal atrophy
- Any other AEs and SAEs
- Information on pregnancy occurrence, outcomes, and lactation (from patients and female partners of patient)
- Ophthalmic examination results for VA, VF, FST, and OCT:

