7.6.2 Voretigene neparvovec safety

Adverse events including the AESIs, SAEs, and pregnancy occurrence and outcome information (including information collected in the Novartis Global Safety database) will be summarized in annual progress reports and the final study report. All AEs and SAEs will be provided in patient data listings. Additional listings, summaries, and graphics may be generated, as appropriate.

Adverse events will be coded to system organ class (SOC) and preferred term (PT) using the Medical Dictionary for Regulatory Activities (MedDRA). The incidence (number and percentage of patients with an AE observed one or more times) and number of events for each AE will be presented for AEs and SAEs, and will be tabulated by SOC and PT, both overall and by severity level and relationship to treatment and/or surgical procedure, as appropriate. This will be performed both for the cumulative duration of follow-up through the analysis time point of interest and/or on an annual basis, the latter to assess the potential, if any, for increasing or decreasing trend in reported AEs. Safety results will be presented by age categories.

Administration of voretigene neparvovec includes the surgical procedures of pars plana vitrectomy followed by voretigene neparvovec injection via bleb formation in the subretinal space. AEs associated with the administration procedures include: increased intraocular pressure, retinal tear, retinal detachment, macular disorders, cataract, and intraocular inflammation and/or infection related to the procedure. A comparative analysis of these ocular AEs between treated patients and published literature data on pars plana vitrectomy will be included in the progress reports.

The incidence of these identified AEs will be summarized descriptively for this study.

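### Annual AE percentages over all FAS patients track follow-up maturity as well as risk, so they cannot show the trend that Section 7.6.2 wants from them

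*Protocol*

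**What the plan says.** Protocol Section 7.6 fixes a general rule for categorical summaries: "Unless otherwise noted, the denominator for the percentages will include all patients in the FAS population". The FAS consists of patients who consented, were enrolled and received at least one injection; time under observation plays no part in it.

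Section 7.6.2 then defines the AE measure: "The incidence (number and percentage of patients with an AE observed one or more times", together with the number of events. It is to be shown cumulatively to the analysis time point, by year, or both. The stated purpose of the yearly display is "the latter to assess the potential, if any, for increasing or decreasing trend in reported AEs". No other denominator is named there, and the text does not say whether a year is counted from injection or is a calendar or reporting year.

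The setting is staggered entry with fixed individual follow-up. Section 7.4: "it is expected that a minimum of 40 adult or pediatric patients can be enrolled over a five-year enrollment period". Section 7.2: "Patients will be followed for five years following administration of voretigene neparovec". Section 7.6 calls for interim data assessments at least annually. The unit of analysis is the patient for non-ocular AEs and the eye for ocular AEs.

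**The concern.** A percentage of all FAS patients is a sound measure of risk in a given year only if nearly all of them were observed through that year. With five-year accrual and annual reporting, that fails at every report until the last patients complete follow-up. A patient injected six months before a data cut cannot contribute an event in years 2 to 5 but is counted in the denominator for each of them. The yearly figures then mix two quantities, the risk and the share of the cohort that has got that far, and the table is meant to be read for a trend in the first.

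Long-term safety is the reason for the study. If late-year percentages are low because few patients have reached those years, a stable risk can look as if it is declining, and a rising risk can be masked. The crude cumulative percentage is understated for the same reason.

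**Working it through.** The protocol gives no AE rate, dropout rate or precision calculation, so there is no figure of its own to reproduce. The question is what the stated rule returns when the truth is known.

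**Inputs from the protocol.** 40 patients; accrual over 5 years (Section 7.4); 5 years of follow-up from administration (Section 7.2); data collection from December 2019 to December 2029 (Section 4), that is 5 + 5 years.

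**Assumptions.** Uniform entry at injection. A constant 10% risk of at least one event in each year, whatever happened earlier; hazard λ = −ln 0.9 = 0.105 per year. Dropout of 0, 5 or 10% per year.

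**Cut at 5 years, no dropout, by year since treatment.** Follow-up is uniform on 0 to 5 years. A share (5 − k)/5 has completed year k and 1/5 is part-way through it. The average risk in a partly observed year is 1 − 0.1/0.1054 = 0.051. The percentage over all FAS patients is therefore

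(5 − k)/5 × 0.10 + 1/5 × 0.051.

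Person-years in year k are 40 × (5 − k + 0.5)/5.

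| Year since treatment | 1 | 2 | 3 | 4 | 5 |
|---|---|---|---|---|---|
| True risk, % | 10 | 10 | 10 | 10 | 10 |
| All-FAS percentage | 9.0 | 7.0 | 5.0 | 3.0 | 1.0 |
| Percentage of patients who entered that year | 9.0 | 8.8 | 8.4 | 7.5 | 5.1 |
| Person-years | 36 | 28 | 20 | 12 | 4 |
| Rate per 100 person-years | 10.5 | 10.5 | 10.5 | 10.5 | 10.5 |

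The ninefold fall hardly depends on the assumed risk: 2% per year reads 1.8 down to 0.2%, and 30% reads 27.2 down to 3.2%.

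**Crude cumulative incidence at the same cut.** The average of 1 − 0.9^u for u uniform on 0 to 5 is 1 − 0.4095/(5 × 0.1054) = 0.22. The true 5-year risk is 1 − 0.9^5 = 0.41.

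**A truly rising risk.** If the annual risk doubles (10, 12.5, 15, 17.5, 20%), multiplying by the observed shares 0.9, 0.7, 0.5, 0.3 and 0.1 gives about 9, 8.8, 7.5, 5.3 and 2%. The table falls while the risk doubles.

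**Cut at 7 years, no dropout.** 10, 10, 9, 7, 5%.

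**Final report (10 years).** With no dropout, 10% in every year: flat. With 10% annual dropout the two hazards are equal, so year k reads 0.5 × (1 − 0.81) × 0.9^(k−1), which is 9.5, 8.55, 7.7, 6.9 and 6.2%; crude cumulative incidence is 0.5 × (1 − 0.81^5) = 33% against 41%. With 5% annual dropout the years read 9.8, 9.3, 8.8, 8.4 and 7.9%.

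**By calendar year, no dropout, over patients enrolled to date.** 5.1, 7.5, 8.4, 8.8, 9.0, 9.0, 7.0, 5.0, 3.0 and 1.0% for calendar years 1 to 10: a rise during accrual and a fall after it, again with constant risk.

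Person-time recovers the constant hazard at every cut and dropout rate. Restricting to patients who entered the interval removes only part of the artefact, because partly observed years still count as whole.

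**The case against.** The denominator is a default that allows exceptions, and Section 7.6 refers to a SAP for the full methods. That SAP is not at hand and could set an at-risk denominator without contradicting the protocol. This stands, and it lowers the certainty. It does not remove the point: Section 7.6.2 states the measure and the trend purpose, and it notes no exception.

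A reader might infer that the tables will always show falling rates. The documents do not support that. The direction depends on what annual means, which Section 7.6.2 leaves open; the final table is flat with complete follow-up; and any final-report fall rests on an assumed dropout rate. Patients treated before the study began are eligible (Section 7.1) and their AEs are collected back to dosing (Section 9.1). They bring late-year experience into early reports and would soften the decline.

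A reader might also infer that late ocular events such as chorioretinal atrophy or cataract are necessarily diluted in this way. The default counts patients, while ocular AEs are analysed by eye, so the ocular denominator is unclear rather than fixed wrongly.

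Nor does the lost-to-follow-up rule in Section 7.2 ("A patient cannot be considered as lost to follow-up until the time point of their scheduled End of Study visit has passed") make matters worse. FAS membership does not depend on follow-up status, so declaring a patient lost sooner would leave an all-FAS percentage unchanged, and the rule does not prevent censoring at last contact.

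Finally, the study is descriptive, the yearly table is one of two permitted displays, and event counts and full listings are also produced. Late events therefore remain visible one by one. Counts and listings do not supply the missing exposure, however, so they do not correct the trend.

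**Conclusion.** The point holds in a limited form. Followed as written, Sections 7.6 and 7.6.2 give annual and cumulative AE percentages that reflect follow-up maturity as well as risk. Under uniform entry, no dropout and a constant 10% annual risk, the 5-year cut shows 9% in year 1 and 1% in year 5, and 22% cumulative incidence where the truth is 41%. By calendar year the same constant risk shows a rise and then a fall. On either reading, interim trends cannot be interpreted as risk. In the final report the distortion is absent with complete follow-up and moderate with 10% annual dropout (9.5% to 6.2%).

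The entry pattern, risk and dropout rates are assumptions. The relative fall at the 5-year cut is nearly independent of the risk chosen, but patients treated before study start would reduce it. Whether the reports carry this artefact depends on the SAP. It is a badly fixed rule that is worth correcting, and it does not invalidate the study.

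**What to change.** In Section 7.6.2, and correspondingly in the SAP:

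- Except annual and cumulative AE and AESI displays from the all-FAS default.
- Define annual as year since injection, of the patient for non-ocular events and of the eye for ocular events.
- Report first events (or events) per 100 patient-years, and per 100 eye-years for ocular AEs, with the number at risk in each interval. The number at risk matters because year 5 holds only about 4 patient-years at a 5-year cut with 40 patients.
- Estimate cumulative incidence by Kaplan-Meier or Aalen-Johansen, censored at last contact.

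Crude FAS counts and percentages can stay alongside. The lost-to-follow-up rule in Section 7.2 needs no change. Injection dates (Table 7-1) and AE start and end dates (Section 9.1) are already collected, and the added displays are descriptive, so they fit Section 7.8.

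The cost is a wording change, one re-programmed table set, and late-year figures that look less favourable. Person-time and censoring do not correct for loss to follow-up that is itself related to outcome.

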7.6.2 Voretigene neparvovec safety

Adverse events including the AESIs, SAEs, and pregnancy occurrence and outcome information (including information collected in the Novartis Global Safety database) will be summarized in annual progress reports and the final study report. All AEs and SAEs will be provided in patient data listings. Additional listings, summaries, and graphics may be generated, as appropriate.

Adverse events will be coded to system organ class (SOC) and preferred term (PT) using the Medical Dictionary for Regulatory Activities (MedDRA). The incidence (number and percentage of patients with an AE observed one or more times) and number of events for each AE will be presented for AEs and SAEs, and will be tabulated by SOC and PT, both overall and by severity level and relationship to treatment and/or surgical procedure, as appropriate. This will be performed both for the cumulative duration of follow-up through the analysis time point of interest and/or on an annual basis, the latter to assess the potential, if any, for increasing or decreasing trend in reported AEs. Safety results will be presented by age categories.

Administration of voretigene neparvovec includes the surgical procedures of pars plana vitrectomy followed by voretigene neparvovec injection via bleb formation in the subretinal space. AEs associated with the administration procedures include: increased intraocular pressure, retinal tear, retinal detachment, macular disorders, cataract, and intraocular inflammation and/or infection related to the procedure. A comparative analysis of these ocular AEs between treated patients and published literature data on pars plana vitrectomy will be included in the progress reports.

The incidence of these identified AEs will be summarized descriptively for this study.

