All AEs from all patients enrolled in the study must be collected and recorded in the study database, irrespective of seriousness or causal association. For patients who have been dosed prior to the enrollment in the registry, all the AEs from the time of dosing upto the time of entry to the registry should also be collected and recorded in the registry database.

The occurrence of AEs should be sought by non-directive questioning of the patient at each visit during the study. AEs may also be detected when they are volunteered by the patient during or between visits or through physical examination, laboratory test, or other assessments. Medical conditions/ diseases ongoing before starting treatment with a study drug are only considered AEs if they worsen after receiving the Novartis drug of interest.

All AEs must be recorded on the AE case report form (CRF) with the following information:

1. the severity grade (mild, moderate, severe)
2. the site (right eye, left eye, both eyes, or non-ocular)
3. its relationship to the voretigene neparvovec (vector and/or transgene), the subretinal injection procedure, the concomitant use of corticosteroids that are administered as part of the treatment, a combination of these procedures and products (suspected/not suspected)
4. its duration (start and end dates or if continuing at final exam)
5. whether it constitutes a SAE

In addition, all reports of the following **special scenarios**, whether or not associated with AEs, are also collected and reported in the same manner as AEs:

- Drug-drug or drug-food interaction
- Drug use during lactation
- Lack of efficacy

- Overdose
- Intentional drug abuse and misuse
- Medication errors including drug maladministration
- Dispensing or prescribing errors
- Drug dependence or addiction
- Withdrawal reaction/ syndrome or rebound symptoms
- Unexpected beneficial effect
- Treatment non-compliance (with clinical symptoms)

A standardized safety questionnaire ([Section 12.1](#)) will be used, in conjunction with clinical observations and ophthalmic examination results, to solicit **Adverse events of special interest (AESI)** information. At each visit the patient should be specifically questioned on each of these AESIs. The AESI will be captured on the AE case report form (CRF).

The following events are designated AESIs:

- Ocular AEs
- Lack of efficacy and/or decline in efficacy over time
- Third-party transmission
- Host immune response

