9.2 Follow-up Information

Recurrent episodes, complications, or progression of the initial event must be reported as follow-up to the original episode, regardless of when the event occurs. This report must be submitted within the same timelines immediately, without undue delay, but under no circumstances later than within 24 hours of the Investigator receiving the follow-up information (Note: if more stringent, local regulations regarding reporting timelines prevail). Any event that is considered completely unrelated to a previously reported one should be reported separately as a new event.

Follow-up information is sent to the same contact person to whom the initial information was sent, stating, where an AE report form is used, that this is a follow-up to the previously reported event and providing the date of the original report. If known, the information missing from the

initial report should be completed. The follow-up information should describe whether the event has resolved or continues, if and how it was treated, whether the patients continued or withdrew from study participation.

In case an SAE is not previously documented in the product information (EU SmPC or local equivalent), a Novartis Patient Safety associate may urgently require further information from the treating physician or other involved health care professional for Health Authority reporting.

In case an adverse event is considered to be of particular interest, a Novartis Patient Safety associate may seek additional information concerning the event. Corresponding questionnaires will then be provided by Novartis Patient Safety to the treating physician or other involved health care professional on a case-by-case basis.

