12.1 Safety Questionnaire

Patient ID: _____

Date of Visit _____

Since the patient's last visit, has s/he experienced:

Ocular Event	No	Yes*, Right Eye (OD)	Yes*, Left Eye (OS)	Yes*, Both Eyes (OU)	Start Date	Ongoing/ End Date
Increased Intraocular Pressure						
Retinal Tear						
Macular Disorders						
• Macular Hole						
• Foveal Dehiscence						
• Maculopathy (e.g., epiretinal membrane, macular pucker)						
• Foveal thinning						
• Loss of foveal function						
Chorioretinal atrophy (e.g. injection site atrophy/treatment emergent progressive atrophy)						
Cataract						
Intraocular Inflammation and/or Infection Related to the Procedure						
Retinal Detachment						
Host Immune Response (Ocular)						
Lack of Efficacy						
Decline in Efficacy over Time						
Other ocular event, specify						

Event	No	Yes*	Start Date	Ongoing/ End Date
New or exacerbated neoplastic event, specify				
Third Party Transmission				
Host Immune Response (Non-ocular)				
New or exacerbated hematologic event, specify				
New or exacerbated neurologic event, specify				

***NOTE: If YES to any of the above, the event(s) MUST be reported as an Adverse Event or Serious Adverse Event and documented in eCRFs**

***NOTE: If yes to any of the above, please provide a narrative of the event(s), including relevant information (e.g., presenting signs or symptoms, relevant associated medical or ocular conditions, concomitant medications, tests performed to assess the event and results, treatment given for the event, etc).**

Event:
 
Narrative:

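### Annual percentages of new cataract reports over a fixed denominator fall even at constant risk; show an at-risk denominator beside the FAS percentage

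*Protocol*

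**What the plan says.** Section 7.6 of the protocol sets the general rule: "Unless otherwise noted, the denominator for the percentages will include all patients in the FAS population". It makes the eye the unit of analysis for ocular adverse events but does not write out an eye denominator.

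Section 7.6.2 defines incidence as "The incidence (number and percentage of patients with an AE observed one or more times) and number of events for each AE". It allows this to be tabulated cumulatively and/or by year, the yearly version being "the latter to assess the potential, if any, for increasing or decreasing trend in reported AEs". Cataract is on its list of adverse events tied to the administration procedure, and for that list it also plans "A comparative analysis of these ocular AEs between treated patients and published literature data on pars plana vitrectomy". No exception to the default denominator is made for cataract.

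Three other places bear on what can be counted as a new cataract:

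- Section 9.2: "Recurrent episodes, complications, or progression of the initial event must be reported as follow-up to the original episode".
- The Safety Questionnaire (section 12.1) asks about the period since the patient's "last visit, has s/he experienced", and has columns for a start date and for ongoing or end date.
- Section 9.1: conditions already present before treatment "are only considered AEs if they worsen after receiving the Novartis drug of interest".

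The selection criteria in section 7.2 contain no lens-status restriction.

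**The concern.** Cataract is an important identified risk of the product (section 5). For an event that an eye can newly have only once, and only while it still has its natural lens, the group able to produce a new report shrinks each year. A fixed denominator does not shrink with it. The yearly percentage then drifts downwards for a reason unrelated to risk, in the very table whose stated use is to look for a trend. A steady risk would look like a falling one, and a modest rise could be hidden.

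A second, separate issue concerns the cumulative percentage. A treated eye that is already non-phakic at injection cannot develop cataract, so including it lowers the per-eye rate.

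**Working it through.** The protocol gives no cataract rate and no lens-status data, and section 7.4 says the study size has no statistical basis, so there is no figure in the plan to reproduce.

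**Inputs**

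- From the protocol: at least 40 patients, five years of follow-up, default denominator of all FAS patients.
- Assumed: both eyes treated (2 × 40 = 80 eyes), no dropout, annual tables that count new reports, constant yearly risk *p* in eyes still at risk, *p* from 2% to 20%.

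**Step 1: depletion in annual tables, all eyes phakic.** The share of eyes still at risk at the start of year *k* is (1 − *p*)^(*k*−1). The fixed-denominator percentage is *p*(1 − *p*)^(*k*−1). The at-risk percentage is *p* in every year.

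For *p* = 10%:

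| Year | Eyes at risk | New cataracts | Of 80 eyes | Of eyes at risk |
|---|---|---|---|---|
| 1 | 80.0 | 8.0 | 10.0% | 10.0% |
| 2 | 72.0 | 7.2 | 9.0% | 10.0% |
| 3 | 64.8 | 6.5 | 8.1% | 10.0% |
| 4 | 58.3 | 5.8 | 7.3% | 10.0% |
| 5 | 52.5 | 5.2 | 6.6% | 10.0% |

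Year 5 relative to year 1 is (1 − *p*)^4: 0.92 at 2%, 0.81 at 5%, 0.66 at 10%, 0.41 at 20%.

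**Step 2: patient level.** The literal default is patients, so the check is repeated there. With two independent eyes, the percentage of patients with a new report in year *k* is 1 − (1 − *p*(1 − *p*)^(*k*−1))². At *p* = 10% this is 19.0%, 17.2%, 15.5%, 14.0% and 12.7%. The fall does not depend on choosing eyes as the denominator.

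**Step 3: could a rise be hidden?** Let yearly risk rise through 10%, 11%, 12%, 13% and 14%. The share still at risk is 1, then 0.90, then 0.90 × 0.89 = 0.801, then × 0.88 = 0.705, then × 0.87 = 0.613. Multiplying each by that year's risk gives 10.0%, 9.9%, 9.6%, 9.2% and 8.6%, a decline on paper.

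**Step 4: cumulative percentage.** Depletion does not touch it: at *p* = 10%, 1 − 0.9^5 = 41.0% of phakic eyes by year 5. If a share *f* of treated eyes is non-phakic at injection, the per-eye figure is multiplied by (1 − *f*). For 0, 4, 8 or 16 of 80 eyes the factor is 1.00, 0.95, 0.90 or 0.80. Per patient, only patients with no phakic treated eye dilute the figure: the factor stays 1.00 if every such case is unilateral, and equals the per-eye factor if all are bilateral.

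**Step 5: size against sampling error.** 8 of 80 has an exact 95% interval of 4.4% to 18.8% (eyes taken as independent), which contains the year-5 value of 6.6%. For 4 of 80 (*p* = 5%) the interval is 1.4% to 12.3%, which contains 4.1%. Only at the top of the assumed range does the fall stand out: 16 of 80 gives 11.9% to 30.4%, against 8.2% in year 5.

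**The case against.** The strongest reply is that risk sets for a single event belong in the SAP. The default holds only unless something else is noted, section 7.6 refers to the SAP for the full methods, and the SAP is not at hand. That limits the point to the default the protocol states. It does not make that default suited to the trend purpose that 7.6.2 gives it.

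Several stronger readings are tempting and are not supported:

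- *The protocol prescribes all treated eyes as the denominator.* It does not. It names FAS patients, and gives the eye only as a unit. All treated eyes is an inference, though the fall appears at patient level too.
- *The annual cataract figures will fall.* Only if annual tables are produced, which is optional, and only if they count new reports. The protocol states no counting rule for them. Section 9.2 is a safety-reporting rule, not a tabulation rule, and the questionnaire's column for ongoing events leaves recounting open. If ongoing events are recounted each year, this fall does not arise.
- *The cataract rate is diluted, or its age-category tables or its comparison with published vitrectomy data are biased, by non-phakic eyes.* Nothing shows that any treated eye is non-phakic, still less that the share differs by age, and the published denominators are not given.

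It can also be said that the stated trend is one in reported events, not in risk, and that a fall in new reports is then shown correctly. That is fair as far as it goes, but a reader of a safety trend will take it as a statement about risk unless the at-risk figure stands beside it. Finally, depletion applies to any event counted once per eye. That is true. Cataract is singled out because lens status also bounds who can have it.

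One practical objection stands in full: removing only affected eyes from the denominator would not give the flat rate in step 1, because eyes not followed in the interval would remain. With enrolment over five years and annual progress reports, that matters. The fix below therefore requires follow-up in the interval.

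**Conclusion.** The point holds as a cheap improvement, not as an error that undermines the study. If new cataract reports are tabulated by year over the default denominator, the percentage falls at constant risk by the factor (1 − *p*)^(*k*−1). That is negligible at 2% yearly risk and reaches 0.66 of the year-1 value by year 5 at 10%. At about 80 eyes and risks of 5% to 10% it lies within sampling error, but its direction is predictable, and the descriptive tables carry no test that would warn the reader. The cumulative percentage is unaffected by depletion and is diluted only by non-phakic treated eyes, whose number is unknown and may be zero.

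The sizes rest on assumed risks, bilateral treatment, complete follow-up and counting of new reports.

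**What to change.** Add to section 7.6.2, in substance:

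> Alongside the FAS percentage, cataract is reported per treated eye phakic at injection, and per patient with at least one such eye. The number of non-phakic treated eyes is shown. Where annual tabulations of new events are produced, the denominator for each interval is treated eyes under follow-up in that interval that are still phakic and have no earlier cataract AE. Phakic eyes with cataract present before injection are kept, because worsening counts as an AE.

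This needs no new data item: surgical history, concomitant procedures and event start dates are already collected. The cost is some site queries on lens status, a smaller denominator and a possibly less favourable cataract rate. If every treated eye is phakic, the cumulative per-eye rate does not change. If the SAP already sets an at-risk denominator for cataract, a cross-reference is enough.
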